10. TREATMENT OF PATIENTS

10.1. Selection and Timing of Dose for Each Patient

Once a patient is enrolled, the appropriate dose of ACE-536 will be administered as an SC injection on Cycle 1 Day 1. Subsequent doses will be administered every 3 weeks on Day 1 of the cycle for up to 87 cycles. Patients may not exceed 87 cycles or 1825 days after first dose, whichever occurs first. The last dose of ACE-536 may not be administered after Day 1825, regardless of the number of cycles completed. Dose reductions may be required for individual patients as outlined in the Patient Dose Modifications Rules ([Section 10.8](#)). If a dose delay is required, the patient will return weekly for assessment of hematology results and AEs until the patient is eligible to receive the next dose of ACE-536. Patients will be asked to return to the clinic for two follow-up visits, occurring approximately 28 days and 56 days after their last dose of ACE-536. Dose level titration increases may also occur for individual patients as outlined in the Individual Dose Titration rules ([Section 10.9](#)). If a patient has a positive ADA result at the last visit, the patient may be asked to return for additional ADA testing every three months, until a negative result is obtained or the result is considered to be stabilized.

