5.7. Efficacy Analyses

No formal hypothesis testing is planned. All efficacy endpoint will be performed using the ITT population.

In general, the below rules apply to the derivations of efficacy endpoints which utilize hemoglobin and RBC transfusion data unless specified otherwise:

- Hemoglobin measurements within 14 days following RBC transfusion will be excluded from the efficacy analysis.
- For each patient, all efficacy endpoints will be derived based on an analysis cutoff day, defined as the last dose + 56 days or the last date from transfusion record data, whichever is earlier.

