5.7.2.2. Time to and Duration of Erythroid Response

Time to and duration of erythroid response will be analyzed for erythroid responders defined as below:

- For NTD patients, mean increase of ≥ 1.0 g/dL from pretreatment hemoglobin during any rolling 12 weeks

- For NTD patients, mean increase of ≥ 1.5 g/dL from pretreatment hemoglobin during any rolling 12 weeks
- For NTD patients, mean increase of ≥ 1.0 g/dL from pretreatment hemoglobin during any rolling 24 weeks
- For NTD patients, mean increase of ≥ 1.5 g/dL from pretreatment hemoglobin during any rolling 24 weeks
- For TD patients, $\geq 33\%$ reduction in RBC transfusion burden compared to pretreatment using 12-week intervals
- For TD patients, $\geq 50\%$ reduction in RBC transfusion burden compared to pretreatment using 12-week intervals
- For TD patients, $\geq 33\%$ reduction in RBC transfusion burden compared to pretreatment using rolling 24-week intervals
- For TD patients, $\geq 50\%$ reduction in RBC transfusion burden compared to pretreatment using rolling 24-week intervals

Time to erythroid response will be defined as the time from the first dose date to the first date of any rolling 12- or 24-week interval achieving above erythroid response.

Duration of erythroid response will be defined as the time from the starting date of the first rolling 12- or 24-week interval achieving response to the last date of the last consecutive rolling 12- or 24-week interval achieving response. When there are multiple disjointed intervals with response, the longest interval will be used. Patients with response ongoing by the analysis cutoff day will be censored.

Both time to and duration of erythroid response will be analyzed as continuous variables and summarized by descriptive statistics. In addition, duration of erythroid response will also be analyzed as a time to event endpoint.

The derivations of time to and duration of erythroid response will be listed for each patient.

Erythroid responders may experience multiple periods of response (≥ 8 weeks, ≥ 12 weeks, or ≥ 24 weeks). For these responders, the number of episodes and cumulative duration will be summarized by NTD and TD separately. As an exploratory analysis, the cumulative duration of the multiple responses will be analyzed using Kaplan-Meier method.

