5.7.2.7. Liver Iron Content (LIC)

MRI for liver iron content (LIC) will be performed. Descriptive statistics of actual values, absolute and percentage change from baseline at post-baseline visits will be presented. The summary will be done by NTD/TD, baseline LIC ≥ 3 and < 3 mg/g dw subgroups and baseline iron chelation therapy (ICT) use (yes vs. no) respectively.

LIC responses will be defined as LIC reduction ≥ 1 mg/g dw at post-baseline visits compared with baseline. LIC response rates along with the exact 95% confidence interval will be estimated for NTD and TD patients respectively, as well as by baseline LIC ($<$ or ≥ 3 mg/g dw) and baseline ICT use (yes vs. no). As an exploratory analysis, LIC change from baseline will be summarized by TD responders and non-responders, where TD responder is defined as 33% reduction in rolling 24 week and 50% reduction in rolling 12 weeks, respectively.

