³⁰ **Cycles 24 through 87:** Patients may not exceed 87 cycles or 1825 days after first dose, whichever occurs first. The last dose of ACE-536 may not be administered after Day 1825, regardless of the number of cycles completed. Procedures and visits for Cycles 24 through 27, 28 through 31, 32 through 35, 36 through 39, 40 through 43, 44 through 47, 48 through 51, 52 through 55, 56 through 59, 60 through 63, 64 through 67, 68 through 71, 72 through 75, 76 through 79, 80 through 83 and 84 through 87 follow the same procedures and visits as scheduled for Cycles 20 through 23, with some exceptions as noted above.

³¹ **DXA for BMD** will be performed at selected sites at C1D1, C9D1, C17D1, C25D1, C33D1, C49D1, C65D1, C81D1 and EOT within a +/- 10-day window for each scan. A DXA for BMD is not required if < 3 months since the previous DXA for BMD, unless clinically indicated.

³² **6MWT for NTD patients** will be performed at selected sites at C1D1, C5D1, C9D1, C13D1, C17D1, C25D1, C33D1, C41D1, C49D1, C57D1, C65D1, C73D1, C81D1 and EOT.

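### The exploratory LIC table groups TD patients by ever having responded, with no landmark, so liver iron measured before a response counts as responder LIC and the label can become likelier with follow-up

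*SAP*

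**What the plan says.** The responder split is the last item of SAP 5.7.2.7. It is introduced as exploratory: "LIC change from baseline will be summarized by TD responders and non-responders, where TD responder is defined as 33% reduction in rolling 24 week". The two definitions together are "33% reduction in rolling 24 week and 50% reduction in rolling 12 weeks, respectively". The same section says earlier, of LIC in general, that "Descriptive statistics of actual values, absolute and percentage change from baseline at post-baseline visits will be presented". The sentence on the split does not itself say whether it is by visit, at EOT, or both.

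Other parts of the SAP fix what a rolling response means:

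- SAP 5.7.2.2 dates a response from "the first date of any rolling 12- or 24-week interval achieving above erythroid response", so one qualifying interval anywhere is enough.
- SAP 5.7 ends the search at a patient-specific day, "defined as the last dose + 56 days or the last date from transfusion record data, whichever is earlier".
- SAP Appendix 4 (footnote 30) limits treatment: "Patients may not exceed 87 cycles or 1825 days after first dose, whichever occurs first".
- SAP Appendix 4 (footnote 7) places LIC scans, at selected sites, at C1D1, C9D1, C17D1 and every eighth cycle to C81D1, plus EOT. Each has a 10-day window either side.
- SAP 4.1 and 5.1 bring in the A536-04 data and baseline for patients who rolled over directly. Appendix 3 gives those patients an A536-04 EOT scan near Day 113.

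The LIC section has no landmark, no time-dependent responder status, no restriction to scans after response and no allowance for length of follow-up. SAP 5.7.2.1 does define fixed-window responses (weeks 13-24 and 37-48), but the LIC split does not use them.

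**The concern.** The groups are formed with information that arises after much of the outcome has been measured. A TD patient whose only qualifying window falls in year 4 is a responder in every row of the table, including the C9D1 scan taken years earlier. This is guarantee-time bias.

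A second effect comes with it. Each patient is searched for a best window over his or her own follow-up and judged against one 12-week baseline, so longer follow-up gives more chances to qualify.

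This appears to be the only planned analysis that relates fewer transfusions to change in liver iron. The ferritin summaries and LIC response rates are not split by erythroid response. Readers are likely to take the table as evidence for that link.

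**Working it through.** The plan states no sample size calculation, LIC effect or responder rate, so there is no design figure to reproduce.

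**1. Calendar.** Protocol 10.1 gives the cycle length: "Subsequent doses will be administered every 3 weeks on Day 1 of the cycle for up to 87 cycles". Day of cycle n, Day 1 = 1 + 21(n − 1).

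- C9D1 = 1 + 8×21 = Day 169
- C17D1 = 1 + 16×21 = Day 337
- C41D1 = 1 + 40×21 = Day 841
- C87D1 = 1 + 86×21 = Day 1807

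Days 169 and 337 match SAP 5.9.1, and Day 1807 matches the schedule of events.

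**2. Windows searched.** The cutoff is the last dose day + 56, if transfusion records run that far. The number of 24-week (168-day) windows is cutoff − 168 + 1.

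| Last dose | Cutoff day | 24-week windows |
|---|---|---|
| C17D1 | 393 | 226 |
| C41D1 | 897 | 730 |
| C87D1 | 1863 | 1,696 |

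The range is 1,696 / 226 = 7.5-fold.

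**3. Scan before response.** The earliest 24-week window ends on Day 168. For a roll-over patient the A536-04 EOT scan, near Day 113, precedes completion of any 24-week response. For a patient counted from A536-06 C1D1, the C9D1 scan precedes every response window that starts later than that scan. This step needs no assumption except that some responses start late.

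**4. How far the label depends on follow-up when nothing changes.** This was simulated with no drug effect, 2 units per transfusion and gamma-distributed intervals. The mean interval was 21 days (4 transfusions × 2 units = 8 units per 84 days), with shape 1/CV² (6.25 at CV 0.4). A responder is a patient whose lowest rolling 12-week total is at most 50% of the baseline total. The interval CV is in neither document, so it is an assumption shown as a range.

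| Interval CV | Responders at 24 weeks | Responders at 5 years |
|---|---|---|
| 0.1 | 0% | 0% |
| 0.2 | about 1% | about 17% |
| 0.3 | about 8% | about 64% |
| 0.4 | about 19% | about 75% |

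Repeat runs agree within a few points. At 12 units per 12 weeks the rise is about 5% to 43% at CV 0.4 and 0% to 0% at CV 0.2. In the 8-unit runs with CV 0.2 to 0.4, 63% to 85% of those labelled over 5 years first qualify with a window starting on or after Day 169.

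**5. The 24-week/33% rule.** A second null simulation used three assumed variability levels: low (CV 0.10, always 2 units), mid (CV 0.20, 1-3 units, 10% slow drift) and high (CV 0.30, 1-3 units, 20% slow drift). From a Day 393 cutoff to a Day 1863 cutoff the responder share goes 0% to 0%, 30% to 62% and 44% to 82%.

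**6. Effect on the LIC contrast.** In the mid and high settings, suppose half the patients leave at a random time. Responders are then followed 267 to 578 days longer on average than non-responders. Add an LIC drift of 0.5 mg/g dw per year, in either direction, unrelated to response. Over 267 days it gives 0.5 × 267/365.25 = 0.37, and over 578 days 0.5 × 578/365.25 = 0.79. Using actual last-scan dates, the contrast is 0.35 to 0.76 mg/g dw, against the SAP's own LIC response threshold of 1 mg/g dw. At one common scan visit the same null gives no contrast, by construction.

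**The case against.** The strongest reply is that 5.7.2.7 describes LIC at post-baseline visits. At a common visit both rows have the same scheduled time since baseline, so unequal follow-up alone yields no difference. This stands. A reader might infer that follow-up length drives the LIC contrast, and the documents do not support that. Follow-up affects who gets the label and, directly, any last-scan or EOT summary. The label percentages are not LIC differences, and the 0.35 to 0.76 mg/g dw figure rests on assumed dropout and drift.

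A reader might also infer that non-responders simply lacked time to qualify. That is too strong. A roll-over patient dosed once in A536-06 near Day 113 has a cutoff near 113 + 56 = Day 169, which allows one full 24-week window if transfusion records run that far. A patient with treatment interruption who reaches the scheduled C9D1 scan has also been observed for about 24 weeks. Longer follow-up gives more chances, but short follow-up does not make qualifying impossible.

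The size may be nil: if transfusion is very regular, no one is labelled by chance. The split is also exploratory, SAP 5.2 plans no hypothesis test, scans are done only at selected sites, and the TD patients are a subset of at most 64. A false test result is therefore not at issue.

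None of this answers step 3. Scans taken before a late response are still reported as responder LIC at common visits.

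**Conclusion.** The concern holds in limited form. The stated rule makes TD responder an ever-responder label that uses data from after the scan, and it sets no landmark. Pre-response LIC is therefore counted under responders. The chance of being labelled can rise with follow-up, from not at all at CV 0.1 to about 19% to 75% at CV 0.4 (8 units per 12 weeks, 50%/12-week rule, no drug effect). The direction of any LIC distortion is not fixed: pre-response scans can dilute a real difference, and unequal follow-up can create a false one, mainly at the last scan or EOT.

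The rule and the scan timing come from the documents. Interval variability, units per transfusion, dropout and LIC drift are assumptions. The consequence is a descriptive table that may mislead, and the change is a cheap improvement.

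**What to change.** Add a week-24 landmark summary to SAP 5.7.2.7 as the main LIC-by-response table:

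- Include TD patients still followed at the end of week 24.
- Classify them by the weeks 13-24 response already derived in SAP 5.7.2.1, at ≥33% and at ≥50%. Time the weeks from the same first dose as the baseline used: A536-04 for direct roll-over patients, A536-06 for patients with treatment interruption.
- Summarize LIC change from baseline by scan visit, using only scans after Day 168 on that clock. This excludes the A536-04 EOT scan, and any C9D1 scan (Day 169, 10 days either side) taken before the landmark.
- The ever-responder table may stay as a labelled supplement, with a note that status uses later data.

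The cost is SAP wording and one table, since all inputs exist. Patients who leave before week 24 are not compared. Later responders count as non-responders in the landmark table, which matters because titration starts at C3D1 and proceeds stepwise. Both landmark groupings use a 12-week window, so the rolling 24-week/33% grouping survives only in the supplement. LIC change from baseline will still include change that occurred before the landmark.

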5.7.3. Exploratory Endpoints

5.7.3.1. Biomarkers Related to TGF- β

Biomarkers hepcidin, GDF8, GDF11, and GDF15 will be presented in the listing.

5.7.3.2. Quality of Life (QoL) Questionnaire

QoL questionnaires including FACT-An and SF-36 will be completed at Day 1 of Cycles 1, 5, 9, 13, 17, 25, 33, 41, 49, 57, 65, 73, 81, and EOT. The scoring algorithms for FACT-An and SF-36 are included in Appendix 1.

Individual subscale scores and total scores will be summarized by visit for FACT-An, FACIT-F, and SF-36. FACIT-F scores will also be summarized by visit for TD and NTD groups respectively. NTD-PRO score will be listed and summarized by visit for NTD group only. All derived subscale and total scores along with all individual responses will be listed for each patient.

Pairwise correlations among 6MWT, FACIT-F, SF-36, and hemoglobin will be evaluated at Week 16 and 48. In addition, correlation between NTD-PRO Tiredness and Weakness domain score and FACIT-F score will be evaluated for the during of study.

5.7.3.3. Other Analysis.

The following additional exploratory endpoints will be presented in listings only:

- Extramedullary hematopoiesis (EMH) mass size by MRI
- Spleen size by MRI (in subset of patients with no prior-splenectomy)
- %change and absolute change of bone mineral density (BMD) raw score and z-score by DXA
- Leg ulcer size (area)
- Change and %change in 6-minute-walk test (6MWT) distance in NTD patients
- Hormone parameters (including estradiol, free testosterone, and total testosterone)

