- 2 **Study procedures** must be done prior to administration of study drug. Note that all windows on visits should be determined relative to the date of the previous dose of ACE-536. For patients without treatment interruption, C1D1 procedures shaded grey may be conducted as part of the EOT visit for study A536-04 and may not need to be repeated for study A536-06. All patients must be assessed for eligibility prior to dosing on C1D1. C1D1 MRI for LIC (at selected sites) and EMH masses (unless site does not have feasibility to perform the assessment) and MRI of the spleen (if no prior splenectomy) can be performed up to 56 days prior to C1D1. If performed as part of standard of care, MRI for LIC, MRI for EMH and spleen size do not need to be repeated. All screening and C1D1 procedure results required to confirm eligibility must be obtained and reviewed prior to study drug administration in A536-06. **On dosing days:** Note that the patient dose must be calculated based on the patient's weight on the day of dosing. Starting dose level for C1D1, dose modification rules and titration rules must be reviewed and implemented prior to dosing as required per protocol (see [Section 10.7](#), [Section 10.8](#) and [Section 10.9](#)). If a dose delay is required per the dose modification rules ([Section 10.8](#)), the patient will not be dosed. The patient will return weekly for assessment of hematology results and AEs until the patient is eligible to receive the next dose of ACE-536 and start the next cycle. The patient should resume the study at the planned dosing cycle (e.g. if the patient missed a dose at C4D1, then they would resume dosing at C4D1 and not skip to C5D1).
- 3 **Medical history:** Medical history for patients with treatment interruption will include medical events occurring after EOS visit in study A536-04 and prior to C1D1 for study A536-06. Medical history for patients without treatment interruption will be taken from study A536-04.
- 4 **Quality of life questionnaires** are required at C1D1, C5D1, C9D1, C13D1 C17D1, C25D1, C33D1, C41D1, C49D1, C57D1, C65D1, C73D1, C81D1 and EOT.
- 5 **Physical exam:** Physical exam should also include an optional evaluation of gonadal size of male patients on C1D1, C5D1, C13D1, C22D1, C30D1, C38D1, C46D1, C54D1, C62D1, C70D1, C78D1 EOT and EOS.

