5.2. General Considerations

Unless otherwise noted, continuous data will be summarized with the following descriptive statistics: number of observations (n), mean, standard deviation (STD), minimum, median, and maximum. Categorical data will be summarized with frequencies (n) and percentages (%). In cases where missing data cause percentages not to sum to 100, a missing data row will be provided. Percentages will use column totals as the denominator unless otherwise indicated. For time to event variables, the Kaplan-Meier curves will be presented if the number of patients is more than 5.

All study data will be included in study data listings. Missing data will generally be treated as missing, not imputed, unless otherwise stated.

Data summaries may also be presented for TD and NTD patients separately as specified. All summaries will be descriptive. No formal hypothesis testing is planned.

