¹⁰ **Pregnancy test** (urine or serum) and menstrual history is required prior to C1D1 for female patients of child bearing potential only.

¹¹ Transfusion history will be collected for 12 months prior to C1D1.

¹² **End of Treatment (EOT):** Should be performed 28 days (\pm 7 days) after the last dose of ACE-536. Patients who discontinue treatment early should complete the end of treatment visit at the time of discontinuation and complete the Day 141 follow up visit 28 days (\pm 7 days) after the EOT visit.

¹³ **End of Study (EOS):** Should be performed 28 days (\pm 7 days) after the Day 113/EOT visit (56 days after the last dose of ACE-536).

¹⁴ **Day 85 \pm 2 days** is the last possible study day that ACE-536 may be administered, regardless of the cycle.

¹⁵ If a **dose delay** is required per the dose modification rules the patient will not be dosed. The patient will return weekly to assess hematology results and adverse events until the patient is eligible to administer the next dose of ACE-536.

¹⁶ If the patient has a positive ADA result at their last assessment, the patient may be asked to return approximately every three months for additional testing until a negative result is obtained or the result is considered stabilized.

¹⁷ MRI for liver iron content will be performed at selected sites.

¹⁸ For the first dose of ACE-536, dosing should occur after a minimum of 7 days post-transfusion; subsequent doses should not be given within 24 hours of transfusion or planned transfusion.

¹⁹ Administration of quality of life questionnaires, including but not limited to FACT-An and SF-36 is required for patients in the expansion cohort only.

²⁰ QoL questionnaires including but not limited to FACT-An and SF-36 should be completed at the EOT visit only for expansion cohort patients who discontinue treatment early.

²¹ Abdominal ultrasound of the spleen is required for patients with no prior splenectomy in the dose escalation cohorts only. Patients in these cohorts with clinical signs of a change in spleen size or abnormality should have an abdominal ultrasound as needed throughout study.

²² Pregnancy test is not required at Day 141/EOS.

²³ Physical exam should include an optional evaluation of gonadal size in males at C1D1, EOT, and EOS visits only.

²⁴ MRI of the chest and abdomen for EMH masses and spleen, DXA for BMD and 6MWT for NTD patients will be performed in the expansion cohort patients only, at selected sites.

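### By-visit quality-of-life summaries with no within-patient change can confuse who contributes with how patients changed, and the Week 16 and 48 correlations have no stated clock

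*SAP*

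**What the plan says.** QoL is an exploratory objective in both documents. SAP 5.7.3.2 states: "Individual subscale scores and total scores will be summarized by visit for FACT-An, FACIT-F, and SF-36". NTD-PRO is summarised by visit for non-transfusion-dependent (NTD) patients, and all derived scores and item responses are listed per patient. The questionnaires "will be completed at Day 1 of Cycles 1, 5, 9, 13, 17, 25, 33, 41, 49, 57, 65, 73, 81, and EOT". Note 4 to the Protocol Section 2 schedule agrees: they "are required at C1D1, C5D1, C9D1, C13D1 C17D1, C25D1", and so on to C81D1 and EOT.

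Under SAP 5.2, continuous data are described by "number of observations (n), mean, standard deviation (STD), minimum, median, and maximum". The same section adds: "Missing data will generally be treated as missing, not imputed, unless otherwise stated".

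Change from baseline is not named for QoL. It is named elsewhere, for example for liver iron content in SAP 5.7.2.7: "Descriptive statistics of actual values, absolute and percentage change from baseline at post-baseline visits will be presented". The iron, erythropoiesis and hemolysis sections do likewise, and SAP 5.7.3.3 lists changes in bone mineral density and the 6-minute walk test (6MWT).

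Three further provisions matter:
- SAP 4.1 analyses A536-04 and A536-06 data together for patients who rolled over directly, and only A536-06 data for interrupted patients.
- SAP 5.1 gives rollovers their A536-04 baseline for every measurement.
- SAP Appendix 3, note 19, says that QoL administration in A536-04 "is required for patients in the expansion cohort only".

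On correlations, SAP 5.7.3.2 says: "Pairwise correlations among 6MWT, FACIT-F, SF-36, and hemoglobin will be evaluated at Week 16 and 48". It names no starting point for the weeks. SAP 5.12.1 leaves analysis windows to be driven by the data and set out in programming specifications.

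**The concern.** A table of scores by visit invites the reader to compare a late row with the first. That comparison measures change only if the same patients stand behind both rows. Here they need not, for two reasons: patients leave over up to 60 months and missing scores are not imputed, and some rollovers may have no pretreatment score. An apparent QoL gain in an open-label study with no control could then be a change in composition.

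The correlations raise a smaller issue. A week number means nothing until its origin is fixed, and patients enter by two routes whose first doses are about 16 weeks apart on the calendar. Two programmers could read the same sentence and correlate different visits in different patients.

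**Working it through.** **1. Visit calendar.** Inputs are the 21-day cycle (Protocol 10.1) and the stated visit days (Protocol Section 2; SAP 5.9.1). The study day of cycle k Day 1 is 1 + 21 × (k − 1), and the week is (day − 1)/7. This reproduces the documents' Day 85 for C5, Day 169 for C9, Day 337 for C17 and Day 1807 for C87. For rollovers, the last A536-04 dose is taken at its nominal Day 85 (SAP Appendix 3), and A536-06 C1D1 follows 28 ± 7 days later. That is 85 + 28 = Day 113, or Week 16 (range 15 to 17). The offset between the clocks is 112 days.

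| QoL and 6MWT visit | A536-06 clock | A536-04 clock, rollovers (each ± 1 week) |
|---|---|---|
| C1D1 | Day 1, Week 0 | Day 113, Week 16 |
| C5D1 | Day 85, Week 12 | Day 197, Week 28 |
| C9D1 | Day 169, Week 24 | Day 281, Week 40 |
| C13D1 | Day 253, Week 36 | Day 365, Week 52 |
| C17D1 | Day 337, Week 48 | Day 449, Week 64 |

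Later QoL visits run every 8 cycles to C81D1 (Day 1681, Week 240 on the A536-06 clock).

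**2. Weeks 16 and 48.** These are Days 113 and 337.
- On the A536-06 clock, Week 48 is C17D1. Week 16 has no QoL or 6MWT visit: C5D1 is 113 − 85 = 28 days before it and C9D1 is 169 − 113 = 56 days after.
- On the A536-04 clock, Week 16 is the rollover visit. Week 48 has none: C13D1 is 365 − 337 = 28 days after it and C9D1 is 337 − 281 = 56 days before.
- If each patient is timed from the first dose in the data that SAP 4.1 analyses, Week 16 is a scheduled visit only for rollovers and Week 48 only for interrupted patients.

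**3. Who contributes, before any dropout.** On the A536-06 clock, the C1D1 row mixes pretreatment scores (interrupted patients, assessed before dosing) with scores about 16 weeks after first dose (rollovers). On the A536-04 clock, expansion-cohort rollovers have a pretreatment score, but dose-escalation rollovers may have none and first appear around Week 16. On either clock, a later row minus the first row is not a within-patient change. The number of dose-escalation rollovers is not given.

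**4. Dropout illustration.** The documents give no QoL SD and no dropout rate, so these are assumptions in SD units. Suppose that no patient's score truly changes, and let ρ be the correlation between the score and staying on treatment. With retention p, the mean among those remaining shifts by ρ × φ(z)/p, where z is the normal quantile at 1 − p. At p = 0.5, φ(0)/0.5 = 0.399/0.5 = 0.798, so ρ = 0.2 gives 0.16 and ρ = 0.6 gives 0.48.

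| Retention | ρ = 0 | ρ = 0.2 | ρ = 0.4 | ρ = 0.6 |
|---|---|---|---|---|
| 90% | 0 | 0.04 | 0.08 | 0.12 |
| 70% | 0 | 0.10 | 0.20 | 0.30 |
| 50% | 0 | 0.16 | 0.32 | 0.48 |
| 30% | 0 | 0.23 | 0.46 | 0.70 |

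**5. What paired change would do.** This was simulated with 2,000,000 patients, 50% retention, no true mean change, within-patient correlation 0.5 or 0.7, and selection correlations of 0.2 to 0.6.
- If staying depends on the stable QoL level, the raw visit mean shifts by 0.11 to 0.40 SD and the paired change by 0.00.
- If staying depends on the patient's own change, the raw mean shifts by 0.06 to 0.24 SD and the paired change by 0.12 to 0.48, which is larger.

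In the second case the baseline mean of those remaining falls. With within-patient correlation 0.5 and selection correlation 0.2, for example, it moves by 0.08 − 0.16 = −0.08 SD. Printing that baseline mean beside the change therefore helps to show the selection.

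**The case against.** The best defence is that QoL is exploratory, nothing is tested, and the plan breaks no promise. Protocol 15.2.3 lists quality of life without the word change, although it uses that word for spleen size, bone density and 6MWT. The markers that do receive change summaries in SAP 5.7.2 are secondary endpoints, and several exploratory endpoints receive listings only. All of this stands, and it limits the importance of the point. It does not make a by-visit table readable as change.

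Several stronger readings are tempting, and the documents do not support them:
- A reader might infer that only raw means will be shown. In fact n, SD, median and range are the default, and every score is listed, so falling numbers are visible and paired changes could be worked out by hand.
- A reader might infer that Weeks 16 and 48 miss the schedule altogether. Each is a scheduled visit on one of the two clocks. What is missing is a stated origin, together with a clock that serves both weeks.
- A reader might infer that an on-drug C1D1 score will serve as the rollovers' baseline. SAP 5.1 assigns them the A536-04 baseline.
- A reader might infer that bias has been shown. Discontinuation reasons in SAP 3.2 include pregnancy and sponsor discretion, which need not relate to QoL, and at ρ = 0 the shift is zero.

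Deferring windows to programming specifications (SAP 5.12.1) is a partial answer on the correlations. A window would have to reach 28 days to capture the nearest visit, and the origin would still be unstated.

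**Conclusion.** The point holds at modest weight and merits a SAP edit before database lock. By-visit QoL summaries without paired change cannot separate patient mix from patient change. The mixture of entry routes follows from the documents alone; how much it matters depends on how many rollovers lack a pretreatment score, which is not stated.

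The dropout component is a possibility, not a finding. Its size rests wholly on assumed retention and correlation: 0.04 to 0.70 SD over the non-zero part of the grid, and nil if leaving is unrelated to QoL. Paired change is not a full remedy, because it fails when leaving depends on change.

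The timing point is firm arithmetic under the nominal schedule: neither the A536-06 nor the A536-04 clock has scheduled QoL and 6MWT visits at both Week 16 and Week 48.

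**What to change.** **QoL summaries.** In SAP 5.7.3.2, keep the by-visit summaries. For FACT-An, FACIT-F, SF-36 and NTD-PRO, add:
- paired change from the pretreatment baseline at each visit, with the number of pairs and the baseline mean of those same patients;
- a baseline rule: the A536-04 pretreatment score for rollovers and the A536-06 C1D1 pre-dose score for interrupted patients, with patients who have no pretreatment score left out of the change columns but kept in the by-visit summaries;
- a sentence saying that change among remaining patients can still be biased if dropout depends on change.

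**Correlations.** Keep them cross-sectional as planned. Replace the week numbers with named visits on one stated clock at which QoL, 6MWT and hemoglobin are all scheduled, for example A536-06 C5D1 and C17D1. Present them by entry route, or add a note, because rollovers at those visits are about 16 weeks further from first dose. Pairs involving 6MWT will cover only NTD patients at selected sites.

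**Cost.** SAP wording and a few extra table columns, with no new data collection. The change columns will hold fewer patients, from a study of at most 64 by the SAP's figure, and some late-visit cells may be very small.
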